# SECTION VII: POTENTIAL RISKS AND BENEFITS

1. **Risks:** Describe the reasonably foreseeable risks, including risks to participant privacy, discomforts, or inconveniences associated with participants participating in the research. *Note:* All studies have the potential for risk, if not physical, there may be psychological, reputational, or financial risks or risks to breach of confidentiality.

*Potential risks to confidentiality:* There is a risk of breach of confidentiality, however we will implement safe guards to prevent this as outlined above in sections related to confidentiality.

*Potential risks of Behavioral therapies:* Although Fathers for Change is a newer approach, other programs and agencies have worked with maltreating parents and their children and used play observations. Additionally, we had no adverse events related to the intervention in our pilot studies of Fathers for Change. Psychological risks are minimal and not different from those of equivalent non-study psychotherapeutic interventions.

Potential risks of Rating scales and questionnaires: To participate in this study, subjects are asked to complete various forms and questionnaires during their initial enrollment, during treatment and post-treatment. All of the questionnaires are standardized and should add no risk to the subjects. Some of the questions are personal in nature and may be upsetting

2. **Minimizing Risks:** Describe the manner in which the above-mentioned risks will be minimized. *Potential risks to confidentiality:* 

Potential risks to confidentiality: As detailed above, every effort will be made to maintain participant confidentiality. Confidentiality with regards to completed research forms will be maintained via numbered reference system maintained by the PI and Project Director. Participants names will appear only on the consent form, HIPPA authorization form and "key" form in a password protected file only accessible by the PI and project director. Subjects who decline participation in the study or those who wish to withdraw from the study can continue in their treatment at the outpatient facilities as they would if they were not approached to participate in a study. As stated above to further protect against potential risks to confidentiality for this population, a Certificate of Confidentiality will be obtained. Participants will clearly be informed of the limits of this confidentiality, which are in cases of suspected child abuse or neglect, and imminent risk for harm to self or others (particularly intimate partner or child).

Potential risks of Behavioral therapies: For the treatment conditions, frequent monitoring (at least weekly) of the participants' clinical status by therapists and research staff will ensure identification and withdrawal from the study of participants who show significant psychological or symptomatic deterioration. If a participant shows significant symptomatic deterioration such that they are a danger to themselves or others or are in need of crisis intervention, the clinician, RA or project manager working with the participant will contact Drs. [name] or [name] immediately. Both are licensed clinical psychologists with extensive clinical experience with IPV offenders, victims and children who have witnessed violence or experienced maltreatment. Drs. [name], and [name] have over 15 years experience working with men with histories of IPV, victims and children who have experienced violence and maltreatment. [name] is also clinical psychologists with decades of experience with clinical populations. Senior clinical supervision will be available at any time a client is being seen. Drs. [name], [name], or will assess the situation and assist with crisis stabilization, treatment planning, or facilitate inpatient psychiatric hospitalization if indicated. Participants who chose to withdraw or not participate in the study will have access to usual care at the facilities where the study is offered.

Rating Scale and Questionnaires. Participants will be instructed that they can choose to skip any question or item if they do not want to answer. All the measures have been used in previous research with this population and in the pilot studies conducted by the PI or her co-investigators. The major disadvantage is the time taken to complete them. Our previous experience indicates that the baseline assessment will take 2 hours. A research assistant will meet with the participant online via zoom independent of their clinician and conduct all assessments. Only participants' code numbers will be recorded on the forms themselves to protect confidentiality. Also, careful efforts aimed at maintaining confidentiality have been effective in previous research, and only participants' code numbers will be recorded on the forms themselves to protect confidentiality. *The study team* (*Drs. [name] and [name]*) have extensive experience collecting IPV related data longitudinally from victims of IPV and have safely done so in previous studies. Procedures recommended in the literature and used in our prior studies of phone/text/email follow-up will be carefully adhered.

Additional Safety and Comfort: All research staff will receive substantial training and supervision to ensure that their interactions with all participants are not only professional, but also warm, friendly, non-confrontational, and respectful to all participants. We will take all precautions to ensure the safety of female co-parents of our male participants including: a) ensuring that partners' responses to all screening items are confidential from one another; b) allowing a male participant to remain in the study even if his female partner declines participation for herself or the child (he will not be informed of her decision instead he will be told the research team has decided to continue

with him individually); c) as outlined in the limits to confidentiality section of the study consent form (see above), in the event of any credible threat (harm towards life) made against a female partner, confidentiality will be breached per legal requirements and she and the police will be notified and informed of the potential danger to her; d) providing all female partners referral numbers to the CT Domestic Violence Services a 24 hour crisis support line and other treatment and community resources as needed if she contacts project staff with concerns. Drs. [name] and [name] all have strong working relationships with the Connecticut Coalition Against Domestic Violence (CCADV) and the services provided by the statewide system of supports for victims of IPV.

Protection of Child Participants: Children will be recruited into this study to participate in father-child observational assessments and for those over 7 answer self-report questions about their mental health symptoms. These will provide an observational measure of father-child interactions providing an additional measure of change related to parenting and child maltreatment risk and child self-report of symptoms to corroborate the parent report data we will collect. Fathers will be able to participate without their children to reduce any risks to the children for retaliation for their lack of participation. Study research assistants will describe the study procedures to the child and ask if they would like to participate. Verbal agreement to participate and behavioral compliance without undue pressure from the father will be taken as assent from children given their young age. If a play session cannot begin once a father and child are at the research center or must be ended, father and child will be compensated for the attempt to provide data to minimize risk to the child for being uncooperative. If a play session does not proceed, the father will continue in the study to Children will participate in free-play using age randomization and treatment assignment. appropriate toys with their fathers for 15 minutes and then complete clean-up of used toys. Research assistants will be observing the session through a one way mirror or video in another room and will be trained to assess children's distress level. If at any time, the child becomes overly distressed from being in the room with their father or wishes to end the session, the session will be stopped and they will be offered their small toy to take home. If ending the session and choosing their toy does not help them calm, Ras will call [name], [name] or . A senior member of the research team will always be available at the time of a father-child assessment in the event of distress of the child. All are licensed clinical psychologists with expertise in child development and child mental health treatment. They will be available to assess any child and provide crisis intervention, make referrals for needed services or treatment and provide support. Given the play focus and limited demands of the assessment, there is limited risk for distress of the child participants.

- 3. **Data and Safety Monitoring Plan:** Include an appropriate Data and Safety Monitoring Plan (DSMP) based on the investigator's risk assessment stated below. (Note: the HSC will make the final determination of the risk to subjects.).
  - a. What is your assessment of the overall risk level for subjects participating in this study? Greater than minimal risk.
  - b. If children are involved, what is your assessment of the overall risk level for the children participating in this study?

Risk to children is minimal as their only participation is in play assessment with their fathers. These assessments will be observed through a one-way mirror.

c. Include an appropriate Data and Safety Monitoring Plan. Examples of DSMPs are

available here http://your.yale.edu/policies-procedures/other/data-and-safety-monitoring-plan- template for

i.	Minimal risk
ii.	Greater than minimal/moderate risk

d. For multi-site studies for which the Yale PI serves as the lead investigator:

- i. How will adverse events and unanticipated problems involving risks to subjects or others be reported, reviewed and managed? Click or tap here to enter text.
- ii. What provisions are in place for management of interim results? Click or tap here to enter text.
- iii. What will the multi-site process be for protocol modifications? Click or tap here to enter text.

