# Initial screen:

Referred fathers will be asked to complete an initial brief screening if they are interested in participation in the study, which will include demographic matching information such as age, ethnicity, city of residence, income, employment history, substance abuse history etc. He will be told that his screening questionnaire will be reviewed, and he will be contacted to set up further assessment sessions if he is found to be eligible. This will provide the opportunity for contact with the mother to conduct phone screening with her related to IPV and assess her willingness for herself and their shared child to participate.

Fathers will be told that their female co-parents (and if different current intimate partners of more than 6 months) will be contacted but they will not be told when (day or time) this will occur. Female co-parent contact information will be provided on the referral from DCF so that fathers are not providing this information, and this will limit the possibility of coercion. The phone screening with female co-parents will include IPV specific questions (e.g. severity of IPV and status of protective orders). If the father is not eligible based on screening due to severe IPV that involves admitted hospitalization or strangulation, or a current full protective order related to his child, he will be informed that he does not meet our demographic criteria based on his initial screening. No mention of contact with mother will be made. If the father agrees to the study and he is eligible following screening of his female co-parent and she agrees to participate to provide information about their shared child, he will schedule a time to complete the second assessment with the child. Fathers will be able to participate even if their co-parent refuses participation of their shared child as long as he meets other eligibility criteria (no severe IPV involving hospitalization, no full contact protective order with child, mother consents to participate in providing symptom

information about their shared child) to ensure there is no coercion or retaliation toward female co-parents for their decisions about child participation.

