NOTE: Is this research proposal designed to enroll children who are wards of the state as potential participants?  $\square$  Yes  $\square$  No

It is possible that the children of some enrolled fathers will be placed in foster care and under the guardianship of the Department of children and families at the time of referral. These children would only be enrolled if there was planned reunification with the father.

7. **Inclusion/Exclusion Criteria:** What are the criteria used to determine participant inclusion or exclusion?

**Inclusion Criteria**. Men who (1) report an incident of IPV (pushing, slapping, kicking) within the last 12 months prior to screening (based on court/police records, partner or self- report); (2) have at least one biological child aged 9 months to 12 years with whom they have contact in person or by phone/facetime etc. at least monthly; (3) are able to complete assessments in English; and (4) agree to have their female coparents (mother of the youngest child) contacted as collateral informants and for consent for participation of their shared child. If a participant has more than one child in the age range, the youngest will be the target of assessment. Female coparents (the

target child's biological mother who does not need to be in a relationship with the father at the time of the study) will be contacted to consent for participation of herself and their shared child. If the coparent declines participation of the child the father may still participate in the study if he meets eligibility criteria to prevent any possible retaliation against co-parents for not consenting to child participation. No information about contact with co-parents or their responses will be provided to the fathers

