### SECTION V: RECRUITMENT/CONSENT AND ASSENT PROCEDURES

# 1. Recruitment Procedures:

a. Describe how potential participants will be identified and contacted, and by whom.

Fathers will be provided information about the study at the time of referral by DCF to the Parent & Family Development Program at Yale or the UCONN Health Center. Contact information for co-parents will be provided by DCF or other referral sourc at the time of the referral (which is current practice). Each father will be recruited and given initial screening by a study RA in person or over the phone. If a father expresses interest, an in-person or virtual Zoom appointment will be scheduled to complete informed consent and baseline measures.

Mothers of the fathers' youngest child will be contacted for initial screening and to assess her willingness to allow participation of herself and their shared child in the study. All research staff reaching out to female co-parents or current intimate partners will be trained on phone recruitment strategies used in previous studies by the PI and others to ensure safety of victims of IPV. These include: 1) asking whether she is free to talk now: 2) asking if it is ok to call back again; 3) asking if it is safe to leave messages on her voicemail or via text; and 4) during informed consent, making a plan for the safest way to contact her for follow-up data collection throughout treatment.

Mothers will be interviewed via zoom or in person on different days and encouraged to ensure their safety by choosing a location where they feel safe and away from the father to take the call. Fathers will not be informed of mothers' agreement to participate or the time or location of any contact the study team has with them. They will complete baseline interviews about their relationship history with the father, IPV in the relationship and the father's child maltreatment risk behaviors (hostility, yelling, spanking) toward the child. Mothers and intimate partner baseline interviews will take approximately 1-1 1/2to complete Mothers will be offered \$50 for completion of baseline interviews.

[name] will not be involved in the consent, recruitment, or enrollment of participants.

16

Are you collecting any information about the individuals prior to their signing a consent form? Yes  $\boxtimes$   $\;$  No  $\square$ 

If yes, indicate what information you will be collecting and how it will be gathered (phone screen, paper questionnaire, etc.)

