# 4. How was this estimate derived?

Phase I: Seventy-five fathers, the female co-parent of their youngest child, and their child will participate for a total of up to 225 participants. We intend to include all 75 fathers assigned to study interventions for intent to treat analysis. The planned sample size of 75 participants who will provide data for inclusion in our intention-to-treat analysis should provide sufficient power to detect clinically meaningful differences between and within treatment conditions as specified in our primary aims. A sample of 63 people provides power of 80% to detect a standardized treatment group differences at 18 weeks of d = 0.45. For purposes of power estimates, we assumed d = 0.45 will represent a potentially meaningful clinical difference in both our primary and mechanism outcomes. In a pilot study examining F4C on participant IPV effect size for outcome was d = 0.86. We will enroll 75 participants to accommodate a 16% loss to follow-up.

Using these procedures in prior studies, our rate of successful follow-up has ranged from 70-90%. With 280 participant families randomized and an aim of at least 70% completion, we expect to have 196 cases with complete treatment and follow-up data.

**4. Process of Consent/Assent** (*NOTE: When a study includes minors, parent provide permission [not consent] for the child's participation, and the child provides assent for participation)* 

Describe the setting and conditions under which consent/assent will be obtained, including parental permission or surrogate permission and the steps taken to ensure participants' independent decision-making.

Fathers will complete informed consent either in person or online via Yale's REDcap data system, in line with guidance on obtaining informed consent during the COVID-19 pandemic. Each will agree to have their female co-parent contacted for consent of participation of their shared child.

Mothers will complete informed consent related to their own participation and the participation of children in which they are the primary guardian. This will be completed online via Yale's REDcap system..

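### A booked child visit and the wording used after a refusal look different to the father, so he can infer the coparent decision that the protocol says he will not learn

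*Combined protocol and SAP*

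**What the plan says.** Three places undertake to keep the coparent's choice from the father.

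- Section IV, item 7 (Inclusion Criteria): "No information about contact with co-parents or their responses will be provided to the fathers".
- Section V, item 1 (Recruitment Procedures): fathers are not to be told of mothers' "agreement to participate or the time or location of any contact the study team has with them".
- Section VII, item 2 (Additional Safety and Comfort, point b) provides for "allowing a male participant to remain in the study even if his female partner declines participation for herself or the child". It adds that "he will not be informed of her decision instead he will be told the research team has decided to continue" "with him individually".

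Other places set out what he knows and what happens next.

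- Section IV, item 3 (Initial screen): "Fathers will be told that their female co-parents (and if different current intimate partners of more than 6 months) will be contacted". If he is eligible and "she agrees to participate to provide information about their shared child, he will schedule a time to complete the second assessment with the child".
- Section V (Process of Consent/Assent), on fathers: "Each will agree to have their female co-parent contacted for consent of participation of their shared child". The inclusion criteria require the same agreement from him.
- The Initial screen text lets him take part if she refuses the child's participation, provided that she consents to give symptom information. Exclusion criterion 7 removes him if she will not give it.

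**The concern.** The purpose of the concealment is stated: no coercion of, or retaliation against, coparents over their decisions. The men enrolled have an incident of partner violence within the past 12 months, and the Reportable Events section lists greater danger to the partner or child among the anticipated adverse events. A safeguard that signals her decision by another route is weaker than the text suggests, and a coparent may rely on it when she decides.

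There is a possible second effect, on the data. She reports on partner violence and maltreatment risk during treatment, and collateral reports inform the masked rating that the protocol names as its primary outcome measure. If she believes that her role is visible, she might report less.

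**Working it through.** No arithmetic applies. The check is to follow each possible decision by the coparent and ask what the father is told or sees.

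**What he knows beforehand.** She will be contacted (Initial screen), and she will be asked to consent for their child (Inclusion Criteria; Process of Consent/Assent). A second appointment with the child is a normal part of baseline, and her consent is sought before it (Baseline assessments). So he knows the question, who answers it, and what should follow a yes.

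**What he then observes.**

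| Her decision | Under the Initial screen text and exclusion 7 | Under Section VII, point b |
|---|---|---|
| Agrees for herself and the child | Enrolled, child visit booked | Enrolled, child visit booked |
| Gives information, declines for the child | Enrolled, no child visit | Enrolled, no child visit, told the team is going on with him alone |
| Declines to give information herself | Excluded; no message is specified for this reason | Remains, told the team is going on with him alone |

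**Reading the table.**

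1. The first two rows differ in whether a visit is booked, under either rule. In the second row Section VII also supplies the distinctive message. Agreement and refusal for the child are therefore distinguishable to him.
2. The protocol links that message to no situation other than her declining. A session that fails because the child does not cooperate is handled separately (Section V, item 5; Section VII, Protection of Child Participants): the father continues to randomization, and no such message is mentioned. He would usually already have had a visit booked, so that case gives a refusal little cover.
3. The third row shows a direct conflict. If she declines for herself, Section IV excludes him and Section VII keeps him. The ineligibility message about demographic criteria is written for severe violence or a protective order concerning the child, not for this reason.
4. Under the Section IV rule, a father who knows or guesses that her cooperation is required could also infer from his own enrolment that she agreed to be an informant. Under the Section VII rule, enrolment alone tells him nothing about her.

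**The case against.** The strongest reply is that the three undertakings govern what staff disclose; they do not guarantee that nothing can be guessed. That is a fair literal reading. Agreement is bound to show in any design that brings a child to a session after the mother consents. This part stands, and it is why the remedy includes saying so plainly. It does not excuse a message that the plan ties to refusal.

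The protocol also has real protections: contact details come from the referral source, mothers are interviewed on different days in places they consider safe, screening answers are confidential between partners, and a safe contact plan is made at consent. These lower her risk but do not affect the contrast shown above. Outcomes also draw on father reports, records and masked coding, so under-reporting by coparents is a plausible bias and not a demonstrated one.

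Some stronger readings are tempting but unsupported.

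- A reader might infer that the wording is used exclusively after refusals. The text attaches it to no other case, but does not say what is said when she cannot be reached or a visit is not arranged.
- A reader might infer that enrolled fathers in general will know she is an informant. That needs the Section IV rule, which Section VII contradicts, and a father who knows or guesses it. Nothing says fathers are told of exclusion 7.
- A reader might take any missing child visit to reveal a refusal. Child assent, guardianship and logistics are other possible reasons. For a child under state guardianship, even a booked visit may not reflect the mother's choice.

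**Conclusion.** The concern holds in a limited form. A father booked with his child and a father told that the team will go on with him alone can infer different decisions by the coparent, despite undertakings in three sections that he will not learn them. This follows from the text under either entry rule. It assumes only that the father remembers what he agreed to and that staff follow the procedures as written.

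Inference from enrolment alone is conditional on the Section IV rule and on his awareness of it. The conflict between Section IV and Section VII over a coparent who declines for herself is a contradiction in the documents whatever one thinks of the disclosure question.

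The size cannot be quantified, because no refusal rate is given. The coparent consent form was not available, so it is unknown whether she is already told what he may infer. The change should be made: the safeguard concerns safety, and the correction is cheap.

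**What to change.** 1. Replace the refusal-linked message in Section VII with one neutral, truthful script for every father whose child is not seen, whatever the reason (coparent, child assent, guardianship, logistics). It could say, for example, that child sessions do not take place for all families and that reasons are not discussed. Tell all fathers this at first contact. The script should not say that the team selects which children to invite, because the plan seeks the youngest eligible child of each father.
2. Reword the undertakings in Section IV item 7, Section V item 1 and Section VII item 2: staff will not disclose her decision, but a scheduled child visit may let him infer it. Check that the coparent consent tells her so.
3. Reconcile the Initial screen text and exclusion criterion 7 with Section VII on whether he may remain if she declines for herself, and specify what he is told in that case.

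The cost is script and consent wording and an IRB amendment. Two limits remain. Her agreement will still be visible when a child session takes place, and the neutral script hides refusals only to the extent that children go unseen for other reasons too.
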